Outcome Measures	To develop a new mHealth smartphone application to engage primary caregivers directly in the active monitoring of their infants' development, and to provide tailored feedback and support for the provision of nurturing care.	To collect data on usability and acceptability of the technology to end users and determine effect size of clinical effectiveness (infant development outcomes). The primary outcome is BSID-4 as a measure of infant developmental outcomes.	To test clinical effectiveness (improved infant development outcomes and caregiving behaviors). The primary outcome is BSID-4 as a measure of infant developmental outcomes. The secondary outcomes are quality of infant-caregiver interaction (NCAST feeding scale) and quality of the home environment (HOME scale).	

- In Aim 1, we will develop a new mHealth smartphone application which can be used to engage primary caregivers directly in the active monitoring of their infants' development, and to provide tailored feedback and support for the provision of nurturing care. Aim 1 will use focus groups, an Agile Design process, and the RE-AIM framework for assessment.
- In Aim 2, we will prospectively assess the implementation characteristics of the technology—usability, acceptability, and sustainability—for caregivers over time for different periods of infant development. Aim 2 will use a prospective, longitudinal, six-month pilot intervention, enrolling 40 caregivers and their infants from birth to 4 weeks of age (using simple randomization to assign them to either the 6-month smartphone intervention (n=20) or control (receipt of printed parenting materials, n=20).
- Aim 3 is similar to Aim 2 only 1) it is adequately powered based on Aim 2 results with 110 participants per group, 2) the developmental outcome (BSID-4) will be measured at 18 months in Aim 3 instead of 6 months in Aim 2, and 3) we will add assessment of quality of infant-caregiver interaction as measured by the Nursing Child Assessment Satellite Training (NCAST) feeding scale and Home Observation for the Measurement of the Environment (HOME scale).

BACKGROUND AND SIGNIFICANCE:

(Brief paragraph summarizing any information important for understanding the study and proposed research procedures)

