Aim 2 Study Design. Two-arm prospective, longitudinal, randomized 6-month pilot intervention. We will assess the implementation characteristics of the smartphone application through a longitudinal, six-month usability trial, to determine caregiver engagement over time and to assess the perceived usefulness of the application. Aim 2 will complement the technical work in Aim 1 by conducting a larger-scale pilot implementation of the caregiver smartphone application. Aim 2 is designed to collect data on usability and acceptability of the technology to end users and determine effect size of clinical effectiveness (infant development outcomes).

Aim 3 Study Design. Two-arm prospective, longitudinal, randomized 18-month intervention with developmental outcomes assessed at 18 months. Aim 3 will determine the effectiveness of a smartphone-based, real-time caregiver feedback intervention to promote positive infant developmental outcomes and improved caregiving behaviors. Aim 3 will test clinical effectiveness (improved infant development outcomes and caregiving behaviors).

Eligibility criteria:

Criteria for all aims of the study will be as follows:

Inclusion Criteria: Consenting first-time caregivers with an infant in the eligible age range (0-4 weeks), singleton, full-term (>37 weeks) birth. For stakeholder interviews and application testing phases, any consenting caregiver with an infant less than 6 months of age and a smartphone, or any Maya Health Alliance staff member who works with infants will be eligible to participate.

Exclusion Criteria: Presence of acute malnutrition/wasting or severe medical illness (heart disease, kidney disease, congenital abnormality), medical need for supplementation of breastfeeding, caregiver not literate (our exploratory feasibility data in preparation for this proposal shows that >95% of first time caregivers in the region are now literate).

Recruitment:

The caregivers participating in both phases (Aim 1, design/formative phase; Aim 2, implementation/trial phase) will be recruited from among first-time caregivers receiving services at a major maternal-child wellness clinic run by Maya Health Alliance out of their main office in Tecpán Guatemala.

For Aim 1, up to 20 caregivers will be recruited in this fashion for formative focus groups. Up to 20 Maya Health Alliance staff will be recruited. All staff who work in early child development and nutrition programs will be eligible. Recruitment will be by word of mouth.

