These participants will then be invited, as they are willing, to participate in the formative agile design phase of the app. Subsequently, in Aims 2 and 3, 40 and 220 (respectively) additional caregiver/infant dyads will be recruited in the same fashion into participate in the prospective implementation trial.

Study Procedures:

Aim 1: **Focus groups:** User perspectives will be collected using a focus group format, facilitated by a research staff at Maya Health Alliance under the supervision of [name], who is fluent in Spanish and Kaqchikel Maya, so that speakers who prefer either language can be included. Convenience samples of caregivers who own smartphones and have infants 0-6 months old will be recruited from Maya Health Alliance clinics, taking care to recruit both male and female caregivers. These will be supplemented by additional focus groups with Maya Health Alliance early child development staff (nurses, technicians, physicians). Four focus groups (1-2 hours in duration) will be conducted, with 5-10 participants each (2 groups caregivers, 2 groups staff). Additional focus groups, up to 5 total, will be held as needed so that preference can be given to those who prefer to conduct the sessions in Spanish or Kaqchikel. During the focus groups, participants will be asked about their opinions around their experience with smartphone applications and understanding of an mHealth application in supporting caregiving. Participants will also be shown and have the opportunity to work with examples of existing parenting/caregiving applications and will be asked to provide feedback on the usefulness of these existing applications.

Aim 2: Two-arm prospective, longitudinal, randomized 6-month pilot intervention. Recruited caregivers/infants will undergo simple randomization to one of 2 arms. The control arm (n=20) will receive printed caregiving materials based on recommendations outlined in Table 2. The intervention group (n=20) will receive the

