
Aim 3: Two-arm prospective, longitudinal, randomized 18-month intervention with developmental outcomes assessed at 18 months. Recruited caregivers/infants will undergo simple randomization to one of 2 arms. The control arm will receive printed caregiving materials based on recommendations outlined in Table 1. The intervention group will receive the smartphone application. Study staff will make an initial home visit (less than an hour) to install the application on the caregiver phone and demonstrate use. "Teach back" demonstration will be used to assure understanding.

Subsequently, in the intervention arm, staff will make visits every 3 months (less than 1 hour duration) to assess functionality of the smartphone and answer questions/reinforce use.

In the control arm, staff will conduct visits every 3 months (less than 1 hour duration) to ask if there are questions about the printed caregiving materials. The smartphone app in the intervention arm will function as described above in Aim 2, including the semi-structured interview. This intervention phase of the study will last 18 months. The NCAST feeding scale and HOME scale will be administered at visits 0, 6 months, 12 months, and 18 months. The BSID-4 will be measured at 18 months (less than an hour in duration). BSID-4 will be completed during separate assessment visits. There will be a total of 8 home visits by research staff (initial visit, 3 month follow-up visits months 1-6 and 1 visit at the end of the study for BSID-4). Also, during the home visits, research staff will also collect the following information: Infant/caregiver demographics, infant's medical history, caregiver poverty scorecard, and infant's measurements and weight. This information will be collected for research purposes only and will be obtained directly from the caregiver.

Primary Outcome:

The primary outcome is BSID-4 as a measure of infant developmental outcomes. It is a standardized assessment of cognitive, motor, and language development. Research staff interact with the child in a standardized way and observe his or her behavior.

Secondary Outcomes:

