The secondary outcomes are quality of infant-caregiver interaction (NCAST feeding scale) and quality of the home environment (HOME scale). The NCAST is a standardized, reliable assessment of quality of caregiver-infant interaction. Administration consists of videotaping up to 5 minutes of the caregiver feeding the infant. The HOME is a 45-item yes/no checklist completed by an observer to measure the quality and quantity of stimulation and support available to a child in the home environment, which we have validated extensively already in rural Guatemala.

Table 2. Evidence-based guidance for infant care domains to be incorporated into smartphone application.		
Care Domain	Key Guidance	Source
Sleep	
 * Infants sleep around 14-16 hours per day during the first 6 months * Sleep in the supine position * Sleep in the same room as the mother to support responsive breastfeeding 	UNICEF - Guidance on Infant Care at Night
Feeding	
 * Exclusive breastfeeding for first 6 months (following WHO guidelines for acceptable medical reasons for substitute feeding) * Breastfeeding on demand (on average approximately 8-12 times/day) * Avoid additional food or drink other than breastmilk * Sleep in the same room as the mother to support responsive breastfeeding 	WHO - Infant and Young Child Feeding
Activity	
 * Play: "Provide ways for your child to see, hear, feel, move freely, and touch you. Slowly move colourful things for your child to see and reach for. Sample toys: shaker rattle, big ring on a string." * Communication: "Smile and laugh with your child. Talk to your child. Get a conversation going by copying your child's sounds or gestures." 	UNICEF – Care for Child Development

Standard of Care

Aim 1 (Focus Groups) does not involve an intervention. Aims 2 and 3 will compare 2 interventions: printed caregiving materials and a smartphone application. Both interventions will be provided in addition to standard care. All subjects will be recruited from MHA clinics and will continue to be eligible for all standard of care health maintenance services in those settings, regardless of their decision to participate in the study. BSID-4 results will be discussed with the parent or legal guardian and any standard of care recommendations made.

Minimization of Risk

To protect confidentiality, the following steps will be taken:

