This was a single-center, individually randomized (1:1 allocation ratio), parallel-group pilot trial to compare use of the smartphone app to printed educational materials. First-time primary caregivers and their infant were eligible to participate if the infant was 0-28 days old at the time of recruitment and a singleton full-term (≥ 37 weeks) birth. Infant exclusion criteria were acute malnutrition (weight-for-length/height Z score ≤ -2 SD using WHO standards), severe medical illness, or medical contraindication to breastfeeding. Caregiver exclusion criteria were inability to read or speak Spanish. Eligible caregivers who did not possess a functioning Android smartphone were given a phone for the duration of the study.

Subjects were recruited by trained research nurses within usual clinical care settings after referral by healthcare providers working at Maya Health Alliance. Verbal consent was obtained following Maya Health Alliance protocol for a minimal-risk study with Indigenous populations as obtaining signatures is not a culturally common practice. Study visits and data collection occurred in the home by trained research nurses, except for the secondary outcome variable (Bayley Scales of Infant Development, Version 4; BSID4; Pearson Assessments, San Antonio, TX, USA) which was collected by consulting psychologists in clinical spaces at Maya Health Alliance.

After enrollment and randomization, caregivers received either the smartphone app, installed with assistance from a study nurse, or printed materials. Brief monthly visits (~ 15 minutes) were conducted monthly for 5 consecutive visits by a study nurse to resolve questions about the app or, in the comparator arm, to resolve any caregiver questions about the printed materials. BSID4 data was collected at enrollment and study exit at 6 months post enrollment.

STATISTICAL ANALYSIS PLAN

Quantitative statistical analysis was conducted using Stata Version 17. Demographic and clinical characteristics of study participants were summarized using means and standard deviations; median and interquartile range; or percentages, as appropriate. For BSID4 outcomes, raw differences between intervention and control arms in composite scores were summarized and adjusted differences calculated using linear regression with adjustments chosen *a priori* for sex of child, caregiver educational level, poverty score, birth weight and change in length for age Z score from 0 to 6 months.

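### The adjusted BSID4 difference conditions on infant growth after randomisation, and the plan does not say whether it or the raw difference leads

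*Combined protocol and SAP*

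**What the plan says.** The Statistical Analysis Plan is a single paragraph. For BSID4, "raw differences between intervention and control arms in composite scores were summarized and adjusted differences calculated using linear regression". Five covariates were fixed in advance: the child's sex, caregiver education, and "poverty score, birth weight and change in length for age Z score from 0 to 6 months". The plan does not rank the two estimates, state an estimand, or give a reason for adjusting for growth during follow-up.

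The Study Protocol (Trial design and participants) recruits infants at 0 to 28 days, gives the app or print after randomisation, and collects BSID4 at enrolment and at six months.

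The Aim 2 Study Design says that the pilot should "determine effect size of clinical effectiveness (infant development outcomes)". The Specific Aims say of Aim 3 that "it is adequately powered based on Aim 2 results with 110 participants per group".

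The status of BSID4 differs within the document. Under Primary Outcome, "The primary outcome is BSID-4 as a measure of infant developmental outcomes". Under Trial design and participants, home data collection applies "except for the secondary outcome variable (Bayley Scales of Infant Development, Version 4".

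**The concern.** Four of the five covariates are fixed at baseline. LAZ change is not: it accrues almost wholly after allocation and ends at about the time of the outcome. Whether its starting point is birth or the enrolment visit makes no difference to this. Choosing it in advance prevents data-driven selection but does not make it a baseline variable.

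The adjusted difference departs from the total effect only if both of these hold:

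1. The app changes growth relative to print.
2. LAZ change is associated with BSID4 given arm and the other covariates, either causally or through unmeasured common causes.

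Where common causes exist, the adjusted difference is not a clean direct effect either.

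The first condition is possible. Background and Significance gives the app a role in growth and nutrition, and Smartphone app design lists feeding recommendations. The documents do not show that it holds.

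At stake is the pilot's effect size. A reader is given two estimates, possibly of different quantities, and no rule for choosing between them.

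**Working it through.** The plan states no figure to reproduce. What can be checked is the timing, which is set out above, and how far the two estimates could differ.

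**Identity.** For least squares on the same infants,

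planned difference = baseline-adjusted difference - (arm difference in LAZ change) x (fitted LAZ-change slope),

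where the arm difference is adjusted for the same baseline covariates. In simulation this held with a maximum error of 2e-15. The shift does not depend on the total effect assumed.

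**Inputs.** From the documents: 20 infants per arm (Table 1, Aim 2). Everything else is assumed:
- unit within-arm variances;
- a, the expected arm difference in LAZ change, in within-arm SDs;
- s, the slope in SD of BSID4 per SD of LAZ change, with s = b + p;
- b, the effect of growth on BSID4;
- p, the product of the loadings of an unmeasured common cause.

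**Expected shift = -a x s.** Simulation used 20 per arm, 20,000 replicates per case, and four null baseline covariates in both models.

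| a | b | p | s | -a x s | Simulated shift (SD) |
|---|---|---|---|---|---|
| 0.1 | 0.2 | 0 | 0.20 | -0.020 | -0.020 |
| 0.3 | 0.3 | 0.16 | 0.46 | -0.138 | -0.139 |
| 0 | 0.3 | 0.16 | 0.46 | 0 | -0.001 |
| -0.3 | 0.3 | 0.16 | 0.46 | +0.138 | +0.137 |
| 0.3 | 0 | 0 | 0 | 0 | +0.001 |
| 0.3 | 0.16 | -0.16 | 0 | 0 | 0.000 |
| 0.3 | 0 | 0.16 | 0.16 | -0.048 | -0.048 |

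In the last row growth has no effect on BSID4, so the direct and total effects are equal. The planned model still misses both, through the common cause alone.

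**Against sampling error.** The standard error at 20 per arm is sqrt(2/20) = 0.316 SD. Then 0.02/0.316 = 6% and 0.138/0.316 = 44%.

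**Coverage of the total effect by the 95% interval, planned versus baseline-only.**
- a = 0.1, s = 0.2: 94.8% versus 95.1%.
- a = 0.3, s = 0.46: 92.9% versus 95.1%.

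**Precision lost by dropping LAZ change.** In closed form the standard error is multiplied by 1/sqrt(1 - r^2), where r is the within-arm correlation: 1.02 at r = 0.2 and 1.13 at r = 0.46. Simulated standard errors, planned versus baseline-only:
- s = 0.2: 0.337 versus 0.339, a rise of about 1%.
- s = 0.46, a = 0: 0.305 versus 0.338, a rise of about 11%.
- s = 0: 0.344 versus 0.335, a fall of about 3%.

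Root mean square error at a = 0.3, s = 0.46 is 0.333 versus 0.332.

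**Residual degrees of freedom**, with 40 infants and one term per covariate:
- planned: 40 - 7 = 33;
- without LAZ change: 40 - 6 = 34;
- with enrolment BSID4 added: 40 - 7 = 33;
- with enrolment LAZ as well: 40 - 8 = 32.

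**The case against.** The strongest reply has five parts.

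- **The raw difference is reported beside the adjusted one.** In a 1:1 randomised trial it estimates the total effect, missing data aside. This stands, and it limits the weight of the point to labelling and model choice in a pilot with no stated hypothesis test.
- **The mechanism is weak.** Controls receive "printed caregiving materials based on recommendations outlined in Table 2", and the feeding advice there is "Exclusive breastfeeding for first 6 months (following WHO guidelines for acceptable medical reasons for substitute feeding)". Complementary-feeding content has little room to act within six months. Expected Benefits mentions growth, but for all participants, not for the app over print. This stands too: the growth difference between arms may be nil.
- **The planned model can be the more accurate one.** In a separate run of 12,000 replicates at s = 0.46, root mean square error for the total effect (planned versus baseline-only) was 0.304 versus 0.336 at a = 0, 0.318 versus 0.337 at a = 0.2, and 0.337 versus 0.336 at a = 0.3. At s = 0.20 the planned model was worse by 3% at most (0.339 versus 0.330 at a = 0.3). This stands as a cost of the change. It does not settle what the planned model estimates.
- **The consequence for Aim 3 is unproven.** This stands. The documents do not show which Aim 2 estimate, if any, was used.
- **Choosing a lead now is post hoc, and offering two candidates leaves the gap open.** The first half is fair and calls for disclosure. The second half does not hold, because in a linear model the raw and baseline-only differences estimate the same total effect.

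**Conclusion.** The concern holds, and it should be fixed. Two things are certain: the adjusted model contains a covariate that develops after randomisation, and the plan names no lead estimate. Whether any distortion occurred is not known, nor is its direction.

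Over the assumed range the shift is under half of one pilot standard error, and it vanishes if the arms grew alike or if LAZ change is unrelated to BSID4 given arm and the other covariates. What the correction gains is a clearly defined estimate, not greater accuracy in 40 infants.

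The point concerns the six-month pilot only; no analysis plan is given for the 18-month trial.

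**What to change.** 1. Name one lead BSID4 estimate: the raw difference or a baseline-only adjusted difference. The raw difference is already in the plan.
2. Take LAZ change out of the main adjusted model. Keep sex, caregiver education, poverty score and birth weight. Preferably add the enrolment BSID4 score, which was collected. Enrolment LAZ, from the baseline anthropometrics, is optional. Neither addition is needed to cure the defect.
3. The analysis is described as already done, so report the re-run beside the planned model, say that it was added later, and label the planned model growth-conditioned and exploratory.
4. Report LAZ change by arm, adjusted for the same baseline covariates, with the fitted LAZ-change slope and on the same infants. A reader can then compute the actual shift. Length is measured at each visit, so the data exist. If the arms grew alike, this will show that the issue was harmless here.
5. State which Aim 2 estimate, if any, informed Aim 3.

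The cost is one regression re-run and a few lines of text. The standard error may rise by about 2% to 13% in closed form (about 1% to 11% in simulation) if the within-arm correlation is 0.2 to 0.46. It falls by about 3% if that correlation is zero.
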